2.5.1.1.2 Fludarabine

Fludarabine will be administered intravenously at a dose of 30 mg/m²/day over 60 minutes for five consecutive days (day -6 to -2; total dose received 150 mg/m²). Actual body weight is to be used to calculate BSA for fludarabine (**Appendix D**). However, for patients > 120% of ideal weight, BSA will be calculated using adjusted weight. On days -6 to -4, fludarabine should be administered after Treosulfan is given. Fludarabine (Fludara®, Berlex Laboratories, Inc., Richmond, CA) is commercially available in the U.S. Details of the product's description, preparation; storage and stability are found in the drug's package insert.

2.5.1.1.3 Thymoglobulin® (Rabbit Anti-Thymocyte Globulin; RATG)

Thymoglobulin® will be administered intravenously over three consecutive days (days -4, -3, -2) at a dose of 1.0 mg/kg on day -4, and then 2.5 mg/kg on days -3 and -2 for a total dose of 6.0 mg/kg. Thymoglobulin® will be given intravenously over a minimum of 6 hours for the first two doses and may be infused over 4 hours for the subsequent dose if there are no clinical concerns per institutional practice. Thymoglobulin (rabbit ATG) doses should be based on actual body weight. On days, -4 to -2, Thymoglobulin® should be administered after fludarabine.

Thymoglobulin premedications and subsequent dosing should follow local institutional practice with suggested recommendation for pre-medication with methylprednisolone, diphenhydramine, and acetaminophen (**Table 3a**). Skin tests are not required prior to Thymoglobulin® administration. We also recommend that medications for significant allergic reactions be available at the bedside in case of allergic reaction per standard of care, institutional practice (**Table 3b**).

Table 3a: Recommended Thymoglobulin Pre-Medications and Subsequent Dosing				
	Pre-Medications 30-60 minutes prior to the start of the thymoglobulin infusion on days -4, -3, and -2.		Subsequent dosing 4 hours after the start of the thymoglobulin infusion. The same doses may be repeated at 8 hours after the start of the thymoglobulin infusion.	
	Pediatric:	Adults:	Pediatric:	Adults:
Methylprednisolone	1 mg/kg/dose IV	1 mg/kg/dose IV	0.5 mg/kg/dose IV	0.5 mg/kg/dose IV
Table 3a: Recommended Thymoglobulin Pre-Medications and Subsequent Dosing				
Diphenhydramine	1 mg/kg/dose IV (max 50 mg)	50 mg IV	1 mg/kg/dose IV (max 50 mg)	50 mg IV
Acetaminophen	12.5 mg/kg/dose PO (max 650 mg)	650 mg PO	12.5 mg/kg/dose PO (max 650 mg)	650 mg PO

Table 3b: Medication Recommendations for Thymoglobulin® Significant Allergic Reactions		
	Pediatric:	Adults \geq 40 kg:
Diphenhydramine	1 mg/kg IV (max 50 mg)	50 mg IV
Hydrocortisone	4 mg/kg IV (max 250 mg)	250 mg IV

Note: Thymoglobulin® is the required preparation of ATG for this study. Patients will not be eligible if the treating center plans to use other preparations of ATG.

2.5.2 Infusion of Marrow or PBSC Product Handling & Infusion

2.5.2.1 Bone Marrow

Bone marrow will be the preferred stem cell source for related and unrelated donors; however, PBSC will be allowed as clinically indicated. Donors will undergo a bone marrow harvest according to institutional practice. Institutional procedures should be followed for requesting and receiving marrow units for infusion. Monitoring immediately prior to, during infusion of bone marrow cells, and thereafter will be according to institutional practice. Pre-medication prior to infusion of bone marrow will be according to institutional practice. The goal total nucleated cell count (TNC) for bone marrow grafts is $\geq 3.5 \times 10^8$ TNC/kg (actual recipient weight).

2.5.2.2 PBSC

PBSC collection and infusion will be according to institutional practice. The goal CD34 cell count for PBSC grafts is $\geq 5 \times 10^6$ CD34/kg (actual recipient weight). The recommended maximum CD34 count is 10×10^6 CD34/kg (actual recipient weight).

2.5.3 GVHD Prophylaxis

GVHD prophylaxis will consist of tacrolimus and methotrexate.

2.5.3.1 Tacrolimus

2.5.3.1.1 Tacrolimus Starting Dose/Administration

1. Tacrolimus will be administered intravenously (IV; oral dosing is not allowed for the initial tacrolimus dose) beginning on day -2 at the following recommended starting dose:
 - a. For patients <18 years old:
 - i. Continuous tacrolimus infusion initial dosing: 0.03 mg/kg/day by continuous IV infusion. Centers may transition from continuous tacrolimus infusion to intermittent tacrolimus dosing (i.e., every 12 or every 8 hours per day) per institutional practice.
 - ii. Intermittent tacrolimus initial dosing: 0.015 mg/kg IV every 12 hours (for an initial total daily dose of 0.03 mg/kg/day) or 0.01 mg/kg IV every 8 hours (for an initial total daily dose of 0.03 mg/kg/day for patients <6 years old).
 - b. For patients \geq 18 years old:
 - i. Continuous tacrolimus infusion dosing: 0.02-0.03 mg/kg/day by continuous IV infusion. Centers may transition from continuous tacrolimus infusion to intermittent tacrolimus dosing (i.e., every 12 hours or every 8 hours) per

institutional practice.

- ii. Intermittent tacrolimus dosing: Tacrolimus should be administered at an initial dose of 0.015 mg/kg IV every 12 hours (for an initial total daily dose of 0.03 mg/kg/day).
2. Initial tacrolimus doses are calculated using actual body weight except for those patients who are greater than 100% ideal body weight in which case calculation of dose using adjusted body weight is recommended (see **Appendix D**).
3. The starting tacrolimus dose may be modified to account for possible drug interactions (e.g., concurrent CYP3A4 inhibitor use) according to institutional practice.
4. The same lumen of the central catheter should be used for all tacrolimus infusions.
5. Monitor closely for an acute allergic reaction for the first 30 minutes after starting tacrolimus IV infusion and at frequent intervals thereafter.

2.5.3.1.2 Serum Tacrolimus Levels

1. The following frequency is recommended for following Tacrolimus levels post-transplant:
 - o Day +1 through day +28: Minimum twice weekly
 - o Day +29 through day +100: Minimum weekly
 - o Day +101 through day +180 or initiation of the tacrolimus taper whichever is later: minimum every other week then monthly per institutional practice
 - o If there are concerns for renal dysfunction, the tacrolimus level should be followed more closely per institutional practice
2. The tacrolimus dose should be adjusted to maintain a suggested tacrolimus level of 5-15 ng/mL.
3. To avoid contamination, all serum tacrolimus levels should be drawn from the central catheter port opposite the lumen used to infuse tacrolimus or peripherally.
4. Dose adjustments are recommended if tacrolimus levels are outside the therapeutic range, or if there is evidence of toxicity that may be related to tacrolimus.
5. Although elevated tacrolimus blood levels are more frequently associated with toxicity (especially renal or hepatic), ***“therapeutic” tacrolimus blood levels may also be associated with toxicity*** (e.g., significant tremors). Therefore, dose decreases are recommended for significant organ toxicities that manifest despite a “therapeutic” tacrolimus level.
6. Patients with severe intolerance of tacrolimus may be placed on cyclosporine (trough level of 200-400 ng/mL).

2.5.3.1.3 Conversion from IV to Oral Dosing

1. The patient may be changed to oral dosing per institutional practice in order to maintain a suggested tacrolimus level of 5-15 ng/mL.
2. ***Children*** generally require a larger total daily dose of tacrolimus by weight than adults. For children < 6 years of age, every 8-hour administration may be required to maintain desirable serum trough levels. For those patients in whom adequate serum trough levels cannot be maintained using intermittent oral or IV dosing, continuous IV infusion may be warranted.

2.5.3.1.4 Tacrolimus Taper

1. In the absence of GVHD, we recommend tapering tacrolimus starting at day +180. The dose should be tapered per institutional practice with a suggested taper of 10% of the day +180 dose each week.
2. In the presence of GVHD, or if the patient is receiving corticosteroids or other therapy for GVHD, we recommend that tacrolimus should NOT be tapered at day +180. We recommend that tacrolimus dosing should be maintained to target therapeutic levels until GVHD has been successfully treated per institutional practice.
3. Tacrolimus may be continued beyond day +180 per the treating physician's discretion if there is mixed donor/host chimerism. Of note, it is common to see mixed T-cell chimerism early post-HCT due to ATG. Historically, the donor T-cell chimerism will rise over the first year.

2.5.3.1.5 Drug Interactions and Recommended Tacrolimus Dose-Modifications:

1. *Review of concomitant medications for potential interactions that may significantly alter serum tacrolimus levels is essential* because tacrolimus undergoes extensive metabolism by the hepatic and intestinal cytochrome P-450 system which may impact toxicity and efficacy of tacrolimus.
2. Subjects should *avoid beverages containing the enzyme bergamottin* (grapefruit juice, Sunny Delight, Fresca, and Squirt) when taking tacrolimus.
3. Tacrolimus is extensively metabolized by the cytochrome P-450 (CYP3A4) system and metabolized products are excreted in the urine.
 - a. Drugs that may increase tacrolimus levels include tri-azole drugs (especially voriconazole, isavuconazonium sulfate, and posaconazole), calcium channel blockers, cimetidine and omeprazole, metoclopramide, macrolide antibiotics, quinupristin/dalfopristin, danazol, ethinyl estradiol, methylprednisolone, and HIV protease inhibitors.
 - b. Drugs that may decrease tacrolimus levels include some anticonvulsants (phenobarbital, phenytoin, carbamazepine), caspofungin, rifampin, and St. John's wort.
4. Recommended Tacrolimus dose-modification in setting of azole therapy: Triazole antifungal medications are expected to increase tacrolimus levels, therefore, dosages of tacrolimus should be adjusted accordingly using the guidelines recommended in **Tables 4 and 5**.

Table 4: Recommended pre-emptive dose reduction of tacrolimus when azoles are initiated at steady state levels of tacrolimus	
Antifungal Medication	Tacrolimus Dose
Voriconazole	67%
Posaconazole	67%
Itraconazole	50%
Table 4: Recommended pre-emptive dose reduction of tacrolimus when azoles are initiated at steady state levels of tacrolimus	
Isavuconazole	25%-50%
Fluconazole	25%

Table 5: Anticipated tacrolimus dose increase when azoles are stopped during concomitant tacrolimus therapy

Antifungal Medication	Tacrolimus Dose ↑
Voriconazole	3-fold
Posaconazole	3-fold
Isavuconazole	3-fold
Itraconazole	2-fold
Fluconazole	1.3-fold

COMMENT: Dose increase may not be necessary for 5-10 days

Note: Although tacrolimus doses may need to be substantially increased when azole therapy is stopped, the azole mediated inhibition of cytochrome CYP3A4 (and other) and P-glycoprotein may take 5-10 days to abate and therefore immediate dose increases are not advised. Rather, tacrolimus dose increases should be cautious and more frequent monitoring of tacrolimus levels is appropriate.

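### The isavuconazole entries of Tables 4 and 5 do not match: a 25%-50% tacrolimus reduction on starting against a 3-fold increase on stopping, with no explanation

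*Protocol*

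**What the plan says.** Protocol Section 2.5.3.1.5 says that triazoles are expected to raise tacrolimus levels and directs sites to adjust the dose using Tables 4 and 5.

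Table 4 is titled "Recommended pre-emptive dose reduction of tacrolimus when azoles are initiated at steady state levels of tacrolimus". Its entries, in per cent, are "Voriconazole 67", "Posaconazole 67", "Itraconazole 50", "Isavuconazole 25%-50" and "Fluconazole 25".

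Table 5 is titled "Anticipated tacrolimus dose increase when azoles are stopped during concomitant tacrolimus therapy". It begins with "Voriconazole 3-fold" and gives the same 3-fold figure for posaconazole and isavuconazole, then 2-fold for itraconazole and 1.3-fold for fluconazole.

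Two other parts of the protocol bear on how these figures are used:

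- The note under Table 5 says that azole inhibition may take 5-10 days to wear off. It advises against raising the dose at once, and asks for caution and more frequent level checks.
- Section 2.5.3.1.2 adjusts tacrolimus to a suggested level of 5-15 ng/mL. Minimum monitoring is twice weekly to day +28 and weekly to day +100, then every other week and later monthly.

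Section 2.5.1.1.1 bars isavuconazole from 72 hours before conditioning until conditioning ends and allows it afterwards, when patients are on tacrolimus. Co-administration is therefore foreseen.

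**The concern.** A site that starts and later stops an azole uses both tables on the same patient. For four of the five drugs the tables work as a pair: the increase on stopping undoes the reduction on starting. For isavuconazole it does not.

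The ranking of the drugs also shifts. In Table 4 isavuconazole sits at or below itraconazole. In Table 5 it sits level with voriconazole and posaconazole. The list of interacting drugs just before the tables also groups it with those two, as agents that especially raise tacrolimus. The protocol does not comment on the difference.

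What is at stake is tacrolimus over-exposure. If the Table 4 figure reflects the interaction, the Table 5 increase on stopping is too large for it. If the Table 5 figure does, the Table 4 reduction on starting is too small for it. On the assumption that exposure is proportional to dose, both cases point towards more tacrolimus than intended. Section 2.5.3.1.2 itself links raised levels to toxicity, especially renal and hepatic.

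**Working it through.** **Inputs.** Reduction *r* on starting comes from Table 4 and factor *f* on stopping from Table 5, both in Protocol Section 2.5.3.1.5.

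**Formulas.**
- Increase that undoes a reduction: 1/(1 − r)
- Reduction that an increase would undo: 1 − 1/f
- Dose after starting and then stopping, as a share of the dose before the azole, with no other change: (1 − r) × f

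**Results.**

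| Azole | r (Table 4) | 1/(1 − r) | f (Table 5) | 1 − 1/f | (1 − r) × f |
|---|---|---|---|---|---|
| Voriconazole | 67% | 1/0.33 = 3.03 | 3 | 66.7% | 0.33 × 3 = 0.99 |
| Posaconazole | 67% | 1/0.33 = 3.03 | 3 | 66.7% | 0.33 × 3 = 0.99 |
| Itraconazole | 50% | 1/0.50 = 2.00 | 2 | 50% | 0.50 × 2 = 1.00 |
| Fluconazole | 25% | 1/0.75 = 1.33 | 1.3 | 23.1% | 0.75 × 1.3 = 0.975 |
| Isavuconazole | 25%-50% | 1/0.75 to 1/0.50 = 1.33 to 2.00 | 3 | 66.7% | 0.75 × 3 = 2.25 to 0.50 × 3 = 1.50 |

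The first four rows reproduce the plan's own figures to rounding and return the patient to 97.5%-100% of the original dose. The isavuconazole row does not: its Table 5 factor lies outside the whole range implied by Table 4, and the product is 150%-225%.

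**Could Table 4 mean a reduction *to* the stated percentage?** The inverse would then be 1/r:
- voriconazole and posaconazole: 1/0.67 = 1.49, against 3 stated;
- itraconazole: 1/0.50 = 2, against 2;
- fluconazole: 1/0.25 = 4, against 1.3;
- isavuconazole: 1/0.50 to 1/0.25 = 2 to 4, against 3.

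The isavuconazole factor would fall inside its range, but three of the other four azoles would no longer match. The table's title also speaks of a dose reduction. This reading does not rescue the pair of tables.

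**What would make 3-fold return to the original dose?** The dose when the azole is stopped would have to be 1/3 of the original. Starting from the Table 4 dose of 50%-75%, that needs a further cut of 1 − (0.333/0.50) = 33% to 1 − (0.333/0.75) = 56%, made on tacrolimus levels while the azole is given. The protocol allows level-guided changes but does not say that such a step is expected for isavuconazole.

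**The case against.** The strongest reply is that the tables need not be inverses. Table 4 is a cut made before the interaction shows in the levels. Table 5 is what is anticipated once the azole is withdrawn. A deliberately partial first cut, followed by level-guided reductions, could sit alongside a larger rise at the end. The protocol never states that one table undoes the other. This stands to the extent that the two entries are not shown to be logically incompatible, so a reader who infers a strict contradiction goes further than the text. It does not remove the inconsistency: no such rationale is given, no other azole is handled that way, and if it is intended it needs to be stated.

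The second reply is that no patient need end on 150%-225% of the original dose. Doses are titrated to 5-15 ng/mL, so the dose at azole withdrawal is the titrated one, and the note under Table 5 calls for delayed and cautious increases. This also stands. The range is a check of one table against the other and does not predict what sites would do. However, the note governs the timing and pace of the increase. It does not change the size given for any drug. The Table 4 cut is by design made before levels can guide it.

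A reader might also infer that the mismatch disturbs GVHD prophylaxis and so biases 1-year GVHD-free, event-free survival. The documents do not support that. They give no figure for how many of the 40 patients would start and stop isavuconazole while on tacrolimus, and no link from this table to endpoint events is shown.

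**Conclusion.** The point holds as an unexplained inconsistency in dosing guidance. The isavuconazole rows of Tables 4 and 5 do not correspond: 25%-50% implies 1.33- to 2-fold, 3-fold is stated, and 3-fold implies about 67%. The other four azoles match to rounding, which makes a slip more likely than a deliberate choice but does not prove it.

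The size, 150%-225% of the original dose against 97.5%-100% for the other azoles, rests on two assumptions: both tables are applied literally, and there is no titration in between. The existing level monitoring and the cautionary note lower the practical risk of over-exposure but leave the mismatch in place. The primary endpoint analysis, sample size, type I error and power are not shown to be affected. The documents do not reveal which of the two entries is in error.

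**What to change.** The clinical team should reconcile the isavuconazole rows of Tables 4 and 5. If the difference is intended, a sentence in Section 2.5.3.1.5 should say why isavuconazole is handled differently on starting and on stopping. Sites should then be notified. This review does not say which figure is right and proposes no dose.

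The cost is one table cell or one explanatory sentence, plus a site memo. No statistical section needs to change.

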2.5.3.2 Methotrexate

2.5.3.2.1 Methotrexate Dose/Administration

Methotrexate (MTX) should be administered as an IV push at a dose of 15 mg/m² on day +1 after transplant and at 10 mg/m² on days +3, +6 and +11. Calculation of m² will be per (**Appendix D**). Actual body weight is to be used to calculate BSA for MTX. However, for patients > 120% of ideal weight, BSA will be calculated using adjusted weight.

The first dose of MTX should be given approximately, but no sooner than, 24 hours after completion of the initial stem cell infusion.

MTX should be dose reduced, given with leucovorin rescue, or held for complications such as severe mucositis per institutional practice.

2.5.4 GVHD Treatment

In the event of the development of either acute or chronic GVHD, therapy will be per institutional practice.

2.5.5 Supportive Care

All supportive care will be given in keeping with institutional practice.

2.5.5.1 Infectious Disease Prophylaxis

Patients will receive infection prophylaxis according to institutional practice. Infection prophylaxis will include, but is not limited to, agents or strategies (e.g., PCR screening and preemptive therapy) to reduce the risk of bacterial, herpes simplex, CMV, HHV-6, EBV, Pneumocystis jirovecii, and fungal infections.

2.5.5.2 Infectious Disease Monitoring

- 1. CMV PCR (peripheral blood):** Day 0 through day +100 (minimum weekly or more often if clinical concerns) and then it is recommended to continue weekly or every other week monitoring of CMV PCR through day +180 due to receipt of serotherapy. Additional monitoring should be per institutional practice for patients with a history of CMV

reactivation or CMV disease post-transplant or for those who remain on immune suppression. Use of letermovir is allowed. Any reactivation and/or CMV disease will be captured in this study.

2. **EBV PCR (peripheral blood):** EBV PCR: Day 0 through day +100 (minimum weekly or more often if clinical concerns) and then it is recommended to continue weekly or every other week monitoring of EBV PCR through day +180 due to receipt of serotherapy. Additional monitoring should be per institutional practice for patients with a history of EBV reactivation or PTLD post-transplant. Treatment of EBV reactivation or EBV-related post-HCT lymphoproliferative disease (PTLD) will be per institutional practice.
3. Monitoring of adenovirus, HHV6 and other viruses will be per institutional practice.

Grade 2 and 3 infections will be reported according to the BMT CTN Technical guidelines.

2.5.5.3 Intravenous Immune Globulin (IVIG)

IVIG administration will be according to institutional practice.

2.5.5.4 Growth Factors

Filgrastim (G-CSF) or biosimilar equivalent may be given per institutional practice.

2.5.5.5 Blood Products

Transfusion thresholds for blood product support will be consistent with institutional practice. All blood products will be irradiated.

2.5.5.6 Management of Graft Failure

Graft failure will be managed as per institutional guidelines.

2.5.5.7 Supportive Care for Treosulfan

In order to prevent skin toxicity especially in diaper bearing children it is recommended to wash the skin which is in contact with urine daily or take brief showers during and 48 hours after Treosulfan. Approximately 30–40% of the total dose of Treosulfan is excreted unchanged in urine and is activated to cytotoxic epoxide structures in an alkaline milieu. Since diaper rashes and perineal ulcers can occur in infants after Treosulfan conditioning, frequent diaper changes are recommended.

2.5.5.8 Management of Thymoglobulin Intolerance

Patients experiencing a new, severe, or life-threatening reaction to ATG and therefore unable or unwilling to receive the full planned cumulative dose will continue to be evaluated for the study, but their conditioning regimen may then be altered as per institutional preference or practice with documentation of the deviation.

2.5.6 Risks and Toxicities

2.5.6.1 General

Except for Treosulfan, the agents being used in the study have been used extensively in the HCT setting and have well defined toxicity profiles. In addition, there are many expected toxicities of allogeneic HCT. The following are examples of toxicities that are serious but not unexpected: Grade 4 cytopenias; neutropenic fever and sepsis; bacterial, fungal, or viral (including CMV, EBV, adenovirus, BK virus among others) infection; severe mucositis; severe GVHD; hepatic SOS; pulmonary toxicities; hemorrhagic cystitis; bleeding without hemodynamic compromise.

Additional potential side effects associated with the transplant in general include constitutional (fever/chills, malaise, fatigue, headache, pain, weakness), cardiovascular (edema, cardiac dysrhythmia, hypertension, thrombosis, cardiac failure), dermatologic (alopecia, rash, pruritus, skin depigmentation or hypopigmentation, photosensitivity), gastrointestinal (anorexia, nausea, vomiting, diarrhea, mucositis, dry mouth), hematologic/Immunologic (myelosuppression, immunosuppression, infections/sepsis, hemorrhage, acute and chronic GVHD, graft failure), hepatic (elevation of liver transaminases and/or bilirubin, SOS, hepatic failure), metabolic (electrolyte abnormalities, hyperglycemia), neurologic (dizziness, confusion, anxiety, depression, rarely seizures, encephalopathy, demyelination), pulmonary (cough, dyspnea, interstitial pneumonitis), and renal/bladder (elevation of BUN and/or creatinine, hemorrhagic cystitis, renal failure).

